9.4 Bashir Endovascular Catheter Use – Procedure Steps

1. **Prepare all r-tPA solutions and IV infusion mixtures in Section 8.3** prior to opening the Bashir™ Endovascular Catheter (BECs). The Bashir™ S-B Endovascular Catheter may be preferred for smaller patients or for treatment of thrombus in the left pulmonary.
2. Prepare the relevant BEC(s) for use:
 - a. Ensure that the infusion basket of the BEC can be expanded and collapsed by moving the actuator on the handle backward and forward while depressing the white button.
 - b. With the basket expanded, flush the basket infusion port with standard flush solution. Observe for flush solution exiting the infusion holes of the basket. Collapse the basket.
 - c. Flush the wire lumen of the BEC observing that flush solution exits the tip of the catheter.
3. Using a .018in x 300cm length steel core non-hydrophilic guidewire, introduce the wire into the central lumen of the long sheath.
4. Backload the BEC onto the 0.018in guidewire and advance towards the long sheath. DO NOT insert the BEC into the sheath.
5. Attach a three-way stopcock to the infusion basket port of the BEC.
6. Commence r-tPA infusion via the stopcock on the basket infusion line connector using an infusion pump. Start the infusion through the BEC PRIOR TO inserting the catheter into the sheath. This is to maintain patency during catheter insertion, advancement, and positioning in the patient.

7. Advance the BEC into the target PA and retract the sheath to expose the basket segment.
8. Do NOT aspirate back from the basket infusion line connector to back bleed. Only maintain forward flow by infusing the r-tPA at the prescribed rate 100cc/hr for unilateral PE and bilateral PE, as stated in Table 2.
9. Keeping the wire in the central wire lumen expand the infusion basket of the BEC.

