20.2.3 Primary Safety Endpoint:

The primary safety endpoint is major bleeding within 72 hours of procedure initiation of r-tPA infusion (the start of the infusion). Bleeding events are classified by the International Society of Thrombosis and Hemostasis (ISTH).

20.2.4 Hypothesis:

The comparator device for Bashir Endovascular Catheter is the EkoSonic Endovascular System (EKOS, Bothell, WA), and results from the study evaluating the safety and efficacy of this device were the basis for the performance goal of 14.9% proposed for this study. The SEATTLE II Study reported a 10% (standard error=2.45%) of moderate to severe bleeding in treated subjects within 72 hours of the treatment initiation. The hypothesis is that the bleeding rate in this study will not exceed $10\% + 2*SE = 14.9\%$. A one-sided, one-sample exact test of a binomial proportion p will be used to test the hypotheses below.

$$H_0: p \geq 0.149$$

$$H_A: p < 0.149$$

The hypothesis test for the primary safety endpoint will not be done at the interim analysis, but only at the end of the study. This test will have a type I error rate of 0.025.

20.2.5 Secondary Endpoints:

Descriptive statistics will be generated for the secondary endpoints listed below. For continuous measures (e.g., Modified Miller Index comparing 48 hours post therapy to baseline), the mean and 95% confidence limits will be calculated, along with the median, standard deviation and range. For frequency outcomes (e.g., device success), results will be reported as the overall frequency of occurrence as well as the percentage of subjects.

1. Device Success: The number of devices with therapy delivered without a device failure.
2. Refined Miller Score as measured on contrast enhanced chest CT (CTA) within 48 hours after the completion of the r-tPA infusion compared to baseline as measured by core lab.
3. All-cause mortality at hospital discharge through 30-day follow-up.

4. SAEs through 30-day follow-up.
5. AEs through 30-day follow-up.
6. UADEs through 30-day follow-up.
7. Recurrent PE through 30-day follow-up.
8. Clinically Relevant Non-Major bleeding: Any sign or symptom of hemorrhage (e.g. more bleeding than would be expected for a clinical circumstance, including bleeding found by imaging alone) that does not fit the criteria for the ISTH definition of major bleeding but does meet at least one of the following criteria:
 - a. Requiring medical intervention by a healthcare professional.

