20.3 Analysis Populations

All enrolled subjects who receive the study treatment will be included in the Intent-to-Treat (ITT) population. The ITT will consist of subjects who both provide informed consent to participate and have the BEC (or first of two BECs for bilateral PE) introduced into the sheath. The modified ITT (mITT) population are evaluable subjects defined as members of the ITT who have data available to assess the primary efficacy endpoint of reduction in RV/LV ratio as measured by contrast-enhanced chest CT (CTA) at screening and RV/LV ratio as measured by contrast-enhanced CTA at 48 hours after completion of r-tPA treatment. The patients comprising the mITT population are evaluable patients. Members of the ITT population who remain in the study long enough to complete the 30-day follow-up period will comprise the Per-Protocol (PP) population.

The mITT population will be used to analyze the primary efficacy endpoint. The ITT population will be used to analyze the primary safety endpoint, as well as all secondary safety and device endpoints that do not require 30 days of follow-up (e.g., device success, clinically relevant non-major bleeding, technical procedural complications). The PP population will be used to analyze secondary endpoints that require 30 days of follow-up: all-cause mortality, SAEs, AEs, UADEs, and recurrent PE through 30-day follow-up).

Up to 125 subjects, in up to 20 sites, will be enrolled and treated, with the objective to have at least 100 subjects complete the 30-day follow-up period, and be included in the primary efficacy analysis. Each site will have an enrollment cap such that no more than 20% (n=20) of participants are enrolled at a single site.

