22.3.2 Device Malfunctions and Non-conformances

There are device malfunctions, or non-conformances, that may impact the patient and prevent treatment with an investigational device. Upon commencement of enrollment, if there are device failures that prevent a total of five (5) subjects across two or more study sites (e.g. site 01 has three (3) device malfunctions, and site 05 has two (2) device malfunctions) from being treated in this study, the study shall be paused for re-evaluation of the device. A root cause analysis will be performed to determine the cause(s) of the device failures and a corrective and preventative action will be implemented.

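### Device success is analysed in the ITT population, which leaves out subjects untreated because the catheter failed before sheath entry, so the reported rate can only be biased upward

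*Combined protocol and SAP*

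**What the plan says.** Sections 6.2.3 and 20.2.5 define the endpoint as "Device Success: The number of devices with therapy delivered without a device failure". For frequency outcomes, with device success as the example, Section 20.2.5 states that "results will be reported as the overall frequency of occurrence as well as the percentage of subjects". The analysis is descriptive, with no performance goal.

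Section 20.3 gives the ITT population to "all secondary safety and device endpoints that do not require 30 days of follow-up (e.g., device success" and similar items). It describes that population in two sentences. The first reads "All enrolled subjects who receive the study treatment will be included in the Intent-to-Treat (ITT) population". The second limits it to consented subjects who "have the BEC (or first of two BECs for bilateral PE) introduced into the sheath".

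Section 9.4 puts several functional steps ahead of sheath entry. The operator must "Ensure that the infusion basket of the BEC can be expanded and collapsed by moving the actuator on the handle backward and forward", flush the infusion basket and watch the holes, flush the wire lumen, and start the r-tPA infusion through the catheter before it goes into the sheath.

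Section 22.3.2 recognises that malfunctions may prevent treatment and pauses the study for "device failures that prevent a total of five (5) subjects across two or more study sites" from being treated. Section 19.2 asks sites to log each device and its disposition.

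**The concern.** A device success rate should count every device on which an attempt was made. Here the denominator opens only once the catheter has passed its bench checks and entered the sheath. A subject whose catheter fails those checks, and who gets no replacement, never enters the ITT population, so the failure never enters the rate.

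No other reported endpoint clearly recovers it. Technical procedural complications are also analysed in the ITT population. The device log and the pause rule record the failure, but neither is linked to the reported rate. Section 6.4.1 places no limit on the number of subjects consented, and its ceiling of 125 applies to subjects enrolled and treated. An untreated subject can therefore be succeeded by another with no trace in the device success result.

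What is at stake is a descriptive device-function result in a study whose objective is to demonstrate the efficacy and safety of this catheter. No test or sample size depends on it.

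**Working it through.** The plan states no rate, goal or sample size for device success, so there is no figure to reproduce. The check has three parts.

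**1. Who is excluded**

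| Event | In the ITT population? | Failure counted in device success? |
|---|---|---|
| Catheter fails a 9.4 step before the sheath; subject not treated | No | No |
| Catheter fails before the sheath; replacement enters the sheath | Yes | Not specified |
| Bilateral PE: first catheter enters the sheath, second fails | Yes | Not specified |
| Catheter enters the sheath, then fails | Yes under the sheath-entry sentence; unclear under the treatment-received sentence if no therapy is delivered | Yes if the subject is in the ITT population |

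Only the first row is a definite exclusion. The treatment-received sentence does not bring that subject back; read literally, it is the narrower of the two.

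**2. Direction and size of the exclusion**

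Let N be the ITT subjects, s those counted as successes, and f the subjects untreated because of a pre-sheath failure.

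- Reported rate: s/N.
- Rate over all subjects in whom a device was attempted: s/(N + f).
- Since f is never negative, s/(N + f) cannot exceed s/N, so the exclusion can only raise the rate.
- With s = N, the overstatement is f/(N + f).

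Inputs: N = 125 (maximum treated) and N = 100 (evaluable target, used only as a lower case), both from Section 20.1. The values f = 1, 4 and 5 are assumptions. Five subjects across at least two sites is the pause trigger in Section 22.3.2, and four cannot reach it.

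| f | N = 125, reported 100% | N = 100, reported 100% |
|---|---|---|
| 1 | 125/126 = 99.2% | 100/101 = 99.0% |
| 4 | 125/129 = 96.9% | 100/104 = 96.2% |
| 5 | 125/130 = 96.2% | 100/105 = 95.2% |

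The overstatement is 0.8 to 3.8 points with 125 subjects and 1.0 to 4.8 points with 100.

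**3. The counting rule for replaced catheters**

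Assume 125 treated subjects and five failed catheters, in five different subjects, each replaced successfully.

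- Per device, all unilateral: 125/(125 + 5) = 96.2%.
- Per device, all bilateral: 250/(250 + 5) = 98.0%.
- Per subject, only the final device counts: 125/125 = 100%.
- Per subject, any failure makes the subject a failure: 120/125 = 96.0%.

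The same events give 96.0% to 100% per subject, depending only on a rule the plan does not state. The subject-level figure can lie above or below the device-level figure, so this part has no fixed direction.

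**The case against.** The strongest reply is that the exclusion is narrow. It applies only when a subject leaves wholly untreated; a failed unit followed by a working one keeps the subject in the ITT population. Untreated cases are not hidden either. They count towards the pause rule, which brings a root cause analysis and corrective action. Section 21.0 lets device malfunctions go to the CEC, and the accountability log records each unit. The endpoint is secondary and descriptive, and every failure count used above is assumed.

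All of that stands, and it limits the importance of the point. It does not put the excluded failures into the reported rate.

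A reader might infer more than the text supports in three respects.

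- That device success is reported only per subject. It is not: the endpoint counts devices, and Section 20.2.5 asks for an overall frequency as well as a percentage of subjects.
- That failed-then-replaced catheters, or a failed second catheter in bilateral PE, drop out. The ITT population selects subjects, not devices, and nothing removes those units. Their scoring is unspecified.
- That the missing counting rule biases the rate upward. Part 3 of the working shows that the direction depends on the rule adopted.

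Finally, the separate SAP (THRO-STAT-2019-01) and the case report form were not in the text reviewed and may define device failure or a counting rule. Section 20.2.6 cites that SAP for missing data and COVID-19, not for device success. A rule there would settle the ambiguity, but it would have to override Section 20.3 to remove the exclusion.

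**Conclusion.** The point holds for one defined group: subjects left untreated because the catheter failed before sheath entry. Section 20.3 excludes them from device success, and the resulting bias can only be upward. Its size is unknown. With one to five such subjects and complete success otherwise, the overstatement is 0.8 to 3.8 points against 125 ITT subjects. If no such failure occurs, it is zero.

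The missing device denominator, the undefined term device failure, and the silence on replaced catheters and mixed bilateral results form a second and lesser point: an ambiguity to close before the data are seen.

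The change is worth making because the exclusion follows from a stated population rule and is cheap to correct. It affects no hypothesis test, alpha level or sample size.

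**What to change.** In Sections 20.2.5 and 20.3:

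- Take device success out of the ITT restriction.
- Report a device-level rate: successful BECs divided by all BECs opened or prepared for a consented subject. Include units that fail the Section 9.4 checks and units that are replaced, taken from the accountability log.
- Report a subject-level rate in which every BEC attempted must succeed, and count subjects untreated because of device failure as failures.
- Define device failure.
- Keep the ITT population for the bleeding endpoints.

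The cost is protocol and SAP wording. Sites already log each device and its disposition under Section 19.2; the sponsor should confirm that the log identifies the subject and the step at which a unit failed. The downside is that the reported rate may be slightly lower.

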6.4.3 Follow-up

The follow-up for each subject will be completed at 30-days post-hospital discharge.

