14.0 ASSESSMENTS REQUIRED JUST PRIOR TO HOSPITAL DISCHARGE

14.1 Assessments

1. **Physical Examination** – The physician will perform a physical examination within eight (8) hours prior to discharge.
2. **AE/SAEs** – Adverse events will be monitored and reported on the CRF post-procedure through discharge.

15.0 30-DAY FOLLOW-UP VISIT POST PROCEDURE

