15.1 Assessments

1. **Physical Examination** – The physician will perform a physical exam at 30-day follow-up visit (± 7 days).
2. **AEs/ SAEs** – All adverse events will be recorded at the 30-day follow-up visit.
3. **COVID-19 Impact** – If, as referenced in section 6.4.4 of this protocol, the subject is unable to attend the 30-Day Follow-Up Visit in person due to COVID-19, the assessment may be done over the phone or by video conference. Documentation of the visit and how it was impacted by COVID-19 must be documented on the CRF. Any visit-related procedure that is not completed for the 30-Day Follow-up Visit under this COVID-19 amendment will be reported as a deviation. **Data Collection**
 1. **Medications** – All antiplatelet, anticoagulant, cardiac medications, and NSAIDs post-discharge will be recorded at this visit.

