17.0 ADVERSE EVENT REPORTING

17.1 Serious Adverse Events

An adverse event is any undesirable experience associated with the use of a medical product in a patient. The event is serious and will be collected when the patient outcome is:

1. Death
2. Life-threatening - Report if suspected that the patient was at substantial risk of dying at the time of the adverse event or use or continued use of the device or other medical product might have resulted in the death of the patient.
3. Hospitalization (initial or prolonged) - Report if admission to the hospital or prolongation of hospitalization was a result of the adverse event.

Emergency room visits that do not result in admission to the hospital should be evaluated for one of the other serious outcomes (e.g., life-threatening; required intervention to prevent permanent impairment or damage; other serious medically important event).

4. Disability or Permanent Damage - Report if the adverse event resulted in a substantial disruption of a person's ability to conduct normal life functions, i.e., the adverse event resulted in a significant, persistent or permanent change, impairment, damage or disruption in the patient's body function/structure, physical activities and/or quality of life.
5. Congenital Anomaly/Birth Defect - Report if you suspect that exposure to a medical product prior to conception or during pregnancy may have resulted in an adverse outcome in the child.
6. Required Intervention to Prevent Permanent Impairment or Damage (Devices) - Report if you believe that medical or surgical intervention was necessary to preclude permanent impairment of a body function, or prevent permanent damage to a body structure, either situation suspected to be due to the use of a medical product.
7. Other Serious (Important Medical Events) - Report when the event does not fit the other outcomes, but the event may jeopardize the patient and may require medical or surgical intervention (treatment) to prevent one of the other outcomes. Examples include allergic bronchospasm (a serious problem with breathing) requiring treatment in an emergency room, serious blood dyscrasias (blood disorders) or seizures/convulsions that do not result in hospitalization. The development of drug dependence or drug abuse would also be examples of important medical events.

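### 30-day mortality and the other 30-day safety endpoints are analysed only in subjects who complete 30 days, so deaths drop out and the mortality table reads about 0% by construction

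*Combined protocol and SAP*

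**What the plan says.** Section 20.3 defines three populations. ITT is, in effect, every consented subject in whom a catheter was introduced into the sheath. mITT is the part of ITT with paired CTA measurements. The third is the completer set: "Members of the ITT population who remain in the study long enough to complete the 30-day follow-up period will comprise the Per-Protocol (PP) population".

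The endpoints are then assigned. The primary safety endpoint, and the secondary safety and device endpoints that need less than 30 days, use ITT. For the rest: "The PP population will be used to analyze secondary endpoints that require 30 days of follow-up: all-cause mortality, SAEs, AEs, UADEs, and recurrent PE". The mortality endpoint in Section 20.2.5 reads "All-cause mortality at hospital discharge through 30-day follow-up".

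Section 20.3 also gives the recruitment aim: up to 125 treated, "with the objective to have at least 100 subjects complete the 30-day follow-up period".

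The end of the period is not fixed. Section 6.4.3 says "The follow-up for each subject will be completed at 30-days post-hospital discharge", whereas the heading of Section 15.0 reads "30-DAY FOLLOW-UP VISIT POST PROCEDURE". Section 6.4.6 gives roughly 30 days counted from consent. Section 15.1 allows the visit a window of 7 days either side.

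**The concern.** Membership of the PP population depends on an outcome, namely being alive and still in the study at the end of follow-up. Using that population to estimate mortality is circular, because the subjects who would form the numerator are removed by definition. Nothing in the text counts a death as completed follow-up. Nothing adds an ITT analysis of these endpoints, and the missing-data sensitivity analyses in Section 20.2.6 are limited to the primary endpoints.

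The SAE table has the same fault. Section 17.1 says of an adverse event, "The event is serious and will be collected when the patient outcome is", and death is first on the list that follows. Every excluded death is therefore also an excluded SAE. AEs, UADEs and recurrent PE in subjects who die, withdraw or are lost disappear in the same way.

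The objective in Section 6.1 is to demonstrate safety as well as efficacy. In a single-arm study these rates are the 30-day safety evidence, and Section 21.0 expects comparison with published data. The plan can also contradict itself in one report. A fatal bleed within 72 hours would count in the ITT primary safety endpoint, while the same death would be absent from the mortality and SAE tables.

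**Working it through.** **The plan's own figures.** Section 20.1 enrols 125 to leave 100 after 20% attrition: 100 / (1 − 0.20) = 125, which reproduces. Section 20.3 aims for at least 100 completers, so up to 125 − 100 = 25 treated subjects could be left out with that target still met. This is a ceiling, not a forecast.

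**Inputs.** N = 125 treated is the planned maximum. The documents give no death or event rate, so the number of deaths d and the SAE counts below are assumptions. Intervals are exact (Clopper-Pearson) 95%.

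**Mortality.** With d deaths before completion and no other losses:

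- ITT rate = d / N
- PP rate = 0 / (N − d) = 0 for any d, with upper limit 1 − 0.025^(1/(N − d))

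| Deaths d | ITT | Exact 95% CI | PP as written | Upper 95% limit |
|---|---|---|---|---|
| 1 | 1/125 = 0.8% | 0.02 to 4.4% | 0/124 = 0% | 2.9% |
| 3 | 3/125 = 2.4% | 0.5 to 6.9% | 0/122 = 0% | 3.0% |
| 5 | 5/125 = 4.0% | 1.3 to 9.1% | 0/120 = 0% | 3.0% |

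If only 100 complete, the PP result is 0/100 with an upper limit of 3.6%. At d = 5 the true proportion among treated subjects (4.0%) lies above the PP upper limit in either case.

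**SAEs, deaths the only losses.** Assume 10 of 125 subjects have an SAE (8.0%; 95% CI 3.9 to 14.2%). Each death is one of the 10, so PP = (10 − d) / (125 − d):

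- d = 1: 9/124 = 7.3%
- d = 3: 7/122 = 5.7%
- d = 5: 5/120 = 4.2%

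**SAEs, 25 non-completers.** If k of the 25 had an SAE, PP = (10 − k) / 100:

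- k = 0: 10/100 = 10.0%, above the ITT figure
- k = 2: 8/100 = 8.0%, equal to it, because 2/25 = 8%
- k = 5: 5/100 = 5.0%, below it

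For mortality the error always runs toward zero. For the other four endpoints its direction depends on who leaves, and the PP table alone does not reveal it.

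**The case against.** The best defence has five parts.

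- **The harms are still captured.** SAEs of any cause are reportable (Section 17.5), all AEs go on the case report form (17.3), and the combined DSMB/CEC reviews them (21.0). Bleeding stopping rules use patient counts (22.2), and fatal bleeding within 72 hours counts in the ITT primary endpoint. All of this stands, and it limits the harm to the five planned summary tables. It does not repair them.
- **The endpoints are secondary and descriptive.** Correct: no hypothesis, alpha or sample size depends on them.
- **Some deaths could stay in.** A subject seen early in the visit window who then dies could be counted. So could one judged complete at 30 days post-procedure if deaths are counted to 30 days post-discharge. This is why the claim is about 0% and not exactly 0%. Early deaths are lost on any reading.
- **The 25-subject case may be pessimistic.** The 20% attrition in Section 20.1 concerns evaluable subjects, meaning those with paired CTAs, and a missed scan is not a missed 30-day visit. Section 15.1 also allows remote visits when COVID-19 prevents attendance. That is fair, and the case is only a ceiling. The mortality result does not need it.
- **A crude ITT rate has its own weakness.** It treats unobserved subjects as event-free and can be too low. This is true, and it is why the number not followed must be reported beside it.

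The separate SAP cited in Section 20.2.6 (THRO-STAT-2019-01) was not among the text reviewed. It might override the rule, but Section 20.3 would still need correcting.

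**Conclusion.** The concern holds. As written, the planned mortality analysis cannot measure mortality: it gives about 0% whether no subjects or several die, and that result does not depend on any assumed count. The sizes do rest on assumption. For 1 to 5 early deaths in 125 treated, ITT mortality of 0.8% to 4.0% would be tabulated as 0%. An assumed SAE proportion of 8.0% would become 7.3% to 4.2% if the only losses were those deaths, or anything from 10.0% to 5.0% if 25 subjects left and none to five of them had an SAE. The primary efficacy and safety tests are untouched. The text should still be corrected before analysis. Analysts who counted the deaths anyway would be departing from the written plan after seeing the data.

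**What to change.** In Section 20.3, and in THRO-STAT-2019-01 if it repeats the rule:

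1. Analyse all five 30-day endpoints in the ITT population already defined.
2. Count every event observed up to the end of the 30-day period or last contact, including events in subjects who die, withdraw or are lost.
3. Report crude rates over all ITT subjects, and state beside each how many were not followed to the end.
4. For mortality, add a Kaplan-Meier 30-day estimate censored at last contact. For recurrent PE, add a cumulative incidence estimate with death as a competing event. These are useful additions; steps 1 to 3 cure the defect.
5. Keep the completer table, labelled as supportive.
6. Reconcile the anchors in Sections 6.4.3, 6.4.6 and 15.0, so that the counting period and completion of follow-up share one definition.

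The cost is wording. The events are already collected for all subjects, so no new data or patients are needed, and alpha, sample size and the primary tests do not change. Mortality, and possibly other rates, may look less favourable than under the present rule.
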